6.1. Study Intervention(s) Administered

The study intervention will be administered via a slow IV infusion over approximately 1 hour by blinded site personnel. The infusion rate may be reduced as deemed necessary if an infusion reaction is observed. Participants will be monitored for at least 4 hours after completion of each infusion. Site must have resuscitation equipment, emergency drugs and appropriately training staff available during the infusion and for at least 4 hours after the completion of the infusion. Participants should not use tobacco products from 1 hour before the start of dosing until after collection of the final PK or PD sample after dosing.

Intervention Name	LY3016859	Placebo
Type	Biologic	Not applicable
Dose Formulation	Lyophilized powder reconstituted with sterile water	0.9% Sodium chloride solution
Unit Dose Strength(s)	75 mg/vial	Not applicable
Dosage Level(s)	750 mg starting dose 500 mg subsequent doses	Not applicable
Route of Administration	1 hour IV infusion	1 hour IV infusion
Use	experimental	placebo
IMP and NIMP	IMP and NIMP	IMP and NIMP
Sourcing	LY3016859 from Lilly If needed, saline for reconstitution of IMP will be site sourced.	Placebo will be procured, packaged, labeled, distributed and dispensed as IMP by Lilly
Packaging and Labeling	The lyophilized powder and sterile diluent for infusion will be provided in separate glass vials. Each vial will be labeled as required per country requirement	Placebo will be provided in a glass vial. Each vial will be labeled as required per country requirement

Abbreviations: IMP = investigational medicinal product; NIMP = non-investigational medicinal product.

6.1.1. Special Treatment Considerations

6.1.1.1. Premedication for Infusions

Premedication for infusions is not planned. However, if an infusion reaction occurs, the study investigator(s) should determine the appropriate premedication for subsequent infusions for that participant.

The investigators and sponsor may decide to use premedication for all participants. They will decide this if the frequency of infusion reactions among participants warrants it.

Any premedications given will be documented as a concomitant therapy (see Section 6.5).

6.1.1.2. Management of Infusion Reactions

All participants should be monitored closely, as there is a risk of infusion reaction and hypersensitivity (including anaphylaxis) with any biological agent.

Symptoms and Signs

Symptoms and signs that may occur as part of an infusion reaction include, but are not limited to fever, chills, nausea, headache, bronchospasm, hypotension, angioedema, throat irritation, rash, pruritus, myalgia, and dizziness.

Site Needs

The clinical site should have necessary equipment and medications for the management of any infusion reaction, which may include but is not limited to oxygen, IV fluid, epinephrine, acetaminophen and antihistamine.

Management of Infusion Reactions

Investigators should grade the severity of the infusion reaction and manage infusion reactions based on standard of care and their clinical judgment. If an infusion reaction occurs, then supportive care should be used in accordance with the signs and symptoms.

This table outlines guidance when a mild to moderate infusion reaction occurs.

If...	Then...
a mild to moderate infusion reaction occurs	the infusion rate should be slowed or stopped depending on the symptoms or signs present. For example, reducing the rate by 50% from 2 mL/minute to 1 mL/minute.
the infusion rate is slowed	
 the infusion should be completed at the slower rate, as tolerated. subsequent infusions may be administered at the discretion of the investigator in agreement with the Lilly medical monitor.
the infusion rate is slowed, and subsequent infusions are continued	the infusion rate must be maintained at the slowest tolerated rate used.

The study intervention infusion should be stopped immediately and permanently if it is an infusion reaction

- with systemic involvement, including, but not limited to significant treatment emergent hypotension, bronchospasm, or wide-spread urticaria
- that does not respond to a slower infusion rate or oral medications
- that is determined as clinically significant by the investigator.

If a participant permanently discontinues from study intervention, they should complete AE monitoring and other procedures as stated in Section 4, Study Design, and the CPMP and OA01 SoAs.

6.2. Preparation/Handling/Storage/Accountability

Study intervention and placebo require refrigeration.

Study intervention and placebo will be prepared and verified by unblinded site personnel.

6.3. Measures to Minimize Bias: Randomization and Blinding

No additional stratification factors are considered for this ISA.

6.4. Study Intervention Compliance

Participants will receive study intervention directly from the investigator or designee, under medical supervision. The date and time of each study intervention administered in the clinic will be recorded in the source documents and case report form (CRF). Administration of intervention and study participant identification will be confirmed at the time of dosing by a member of the study site staff other than the person administering the study intervention.

6.5. Concomitant Therapy

All concomitant therapies that are part of routine care for other comorbidities besides OA, are allowed and can be used during the study, if it is permitted based on the inclusion and exclusion criteria.

A list of medications that are prohibited from Visit 2 to Visit 801 for participants randomized to this ISA study will be provided. Participants may return to their standard-of-care after Visit 801 is completed, as clinically appropriate.

7. Discontinuation of Study Intervention and Participant Discontinuation/Withdrawal

Protocol CPMP provides the reasons and procedures for discontinuation of intervention and participant discontinuation that must be followed for this study. LY3016859 specific information is included here.

7.1. Discontinuation of Study Intervention

If the investigator, after consultation with the sponsor-designated medical monitor, determines that a systemic hypersensitivity reaction or a serious infusion reaction has occurred related to study intervention administration, the participant should be permanently discontinued from the study intervention.

A participant should be discontinued from study intervention if they experience a dermatological adverse reaction, such as acneiform rash, that is related to study intervention, **and** is either mild to moderate and does not respond to topical treatment **or** is severe. The participant may continue in the study at the discretion of the investigator in consultation with the medical monitor or study sponsor physician/scientist.

8. Study Assessments and Procedures

Study procedures and their timing are summarized in the protocol CPMP, OA DSA CPMP(1), and ISA OA01 SoAs.

LY3016859 specific assessments and procedures are described here.

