2.3.1. Risk Assessment

Potential Risk of Clinical Significance	Summary of Data/Rationale for Risk	Mitigation Strategy
Study Intervention LY3016859		
Development of treatment-emergent anti-drug antibodies (TE ADA).	Incidence of TE ADA was 50% after a single dose, and up to 57% after multiple doses.	Collect samples up to 20 weeks after last dose to characterize ADA profile.
IV infusion may be associated with infusion reactions and hypersensitivity reactions.	LY3016859 is a monoclonal antibody that will be administered via IV infusion. Hypersensitivity reactions and infusion reactions may occur during treatment with such agents.	Monitor infusion reactions and hypersensitivity reactions. Guidance on management of infusion and hypersensitivity reactions are in Sections 8.2.1. and 8.2.2.
Dermatological adverse reactions similar to EGFR antagonists	One healthy participant who received a single dose of 1 mg LY3016859 experienced a rash that was considered similar to those associated with EGFR antagonists.	Collect dermatological AEs. Stop dosing for severe dermatological AEs.
Changes in eGFR in participants with diabetic nephropathy (DN)	A modest and non-statistically significant decrease in eGFR was observed in participants with DN who received LY3016859 in Part B of Study TGAB, but not in healthy participants in Study TGAA.	Exclude participants with moderate or severe renal impairment in the study. Short dosing duration. Monitor eGFR and stop dosing if necessary. CCI [REDACTED]
Fetal harm due to in utero exposure	No effects on embryo-fetal development in enhanced pilot embryo-fetal development studies in rats and rabbits. Definitive developmental and reproductive toxicity studies are not yet completed.	Do not enroll women who are pregnant or breastfeeding in studies for LY3016859.
Study Procedures		
Participant may experience increased OA symptoms.	Medications that relieve OA pain will not be allowed until Visit 801.	Rescue medication is permitted. Standard treatment of OA may be restarted after Visit 801 based on investigator discretion.

Abbreviations: ADA = anti-drug antibodies; AE = adverse events; DN = diabetic nephropathy; EGFR = epidermal growth factor receptor; eGFR = estimated glomerular filtration rate; IV = intravenous; OA = osteoarthritis; TE = treatment emergent; TGAA = study I5V-MC-TGAA; TGAB = study I5V-MC-TGAB.

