2.3.3. Overall Benefit: Risk Conclusion

The measures taken to minimize risk to participants in this study and the potential risks identified in association with ISA OA01 are justified by the anticipated benefits to participants with OA.

3. Objectives and Endpoints

The master protocol CPMP and OA DSA CPMP(1) include objectives and endpoints applicable for this study. This table describes objectives and endpoints specific for LY3016859.

Objectives	Endpoints
Tertiary/Exploratory	
Characterize the pharmacokinetics and pharmacodynamics of LY3016859 after multiple intravenous infusions in participants with osteoarthritis	Assessment of serum concentrations of LY3016859 and epiregulin to enable pharmacokinetic and pharmacodynamic evaluations
Characterize immunogenicity of LY3016859	Appearance of anti-drug antibodies and neutralizing antibodies to LY3016859
Explore the effect of LY3016859 on the kidney	Assessment of 
 • urine albumin/creatinine ratio • urine protein/creatinine ratio • eGFR

Abbreviations: eGFR = estimated glomerular filtration rate.

4. Study Design

Master protocol CPMP describes the overall study design and study design rationale. This section describes visits and overall procedures unique to ISA OA01 for LY3016859 in addition to the procedures outlined in CPMP and CPMP(1).

Double-blind Treatment Period (Visits 3 through 7)

Each visit is an outpatient visit.

At Visit 3

- participants are randomized to LY3016859 or placebo
- the site completes the OA01 baseline procedures and sample collection
- participants receive their first dose of study intervention via IV infusion over 1 hour
- the site observes participants in the clinic for at least 4 hours after the completion of the IV infusion
- the site completes all post-treatment sample collection and safety monitoring, and
- the site instructs participants to continue with study restrictions and Numeric Rating Scale (NRS) diary entries before their visit discharge.

At Visits 4 through 6

- the site reviews available safety data and completes pre-dose procedures and sample collection
- participants receive an IV infusion over 1 hour
- the site observes participants in the clinic for at least 4 hours after the completion of the IV infusion
- the site completes all post-treatment sample collection and safety monitoring, and
- the site instructs participants to continue with study restrictions and NRS diary entries before their visit discharge.

At Visit 7

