8.1.1. Physical Examinations

Targeted physical examinations of skin, eyes, mouth, lungs and GI tract will be performed at each visit as described in the SoA. Any clinically significant abnormal physical examination findings will be reported as AEs.

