8.2.3. Adverse Events of Special Interest

Dermatological adverse reactions

EGFR antibodies or EGFR-associated tyrosine kinase inhibitors are associated with various dermatological AEs, including acneiform rashes, xerosis, pruritis, and photosensitivity. Secondary infection can also develop.

Participants should use sun protection during the study period. Dermatological adverse reactions should be managed by the investigator according to standard of care. Discontinuation of treatment may be considered if these AEs do not respond to topical treatment or are widespread (>30% body surface area) or are severe.

If any of these AEs are reported, sites will be prompted to provide additional information.

Renal Function

Changes in eGFR were observed in participants with diabetic nephropathy in Study TGAB (Section 2.2). Such changes were reversible and were not associated with increase in proteinuria. Blood and urine samples will be collected to characterize the effects of LY3016859 on renal function and eGFR will be monitored during the study.

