### General Adverse Event Information

- Serious adverse events related to study treatment
- Study discontinuation due to adverse event
- Treatment discontinuation due to adverse event

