**Dermatological**

- Serious or severe dermal reactions

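### For related skin reactions that are severe or do not respond to topical treatment, Protocol 7.1 directs that dosing stop, while Protocol 8.2.3 only permits it

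*Protocol*

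**What the plan says.** Three places in the protocol say what to do about dosing when a skin reaction occurs.

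- **Section 7.1 (Discontinuation of Study Intervention):** "A participant should be discontinued from study intervention if they experience a dermatological adverse reaction, such as acneiform rash". Two conditions follow. The reaction must be related to study intervention, and it must be either severe, or mild to moderate without response to topical treatment. The section then gives the investigator discretion, in consultation with the sponsor's physician or monitor, over whether the participant stays in the study. That discretion does not extend to continued dosing.
- **Section 8.2.3 (Adverse Events of Special Interest):** EGFR antibodies and EGFR-associated tyrosine kinase inhibitors "are associated with various dermatological AEs, including acneiform rashes, xerosis, pruritis, and photosensitivity". Management is left to the investigator under standard of care, and discontinuation of treatment "may be considered if these AEs do not respond to topical treatment or are widespread (>30% body surface area) or are severe".
- **Section 2.3.1 (Risk Assessment):** the mitigation listed for EGFR-antagonist-like skin reactions includes "Stop dosing for severe dermatological AEs".

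Two other provisions bear on how the rule is applied. Before each infusion at Visits 4 to 6 (Protocol Section 4), "the site reviews available safety data and completes pre-dose procedures and sample collection". Section 8.1.1 adds: "Targeted physical examinations of skin, eyes, mouth, lungs and GI tract will be performed at each visit". On the analysis side, SAP 6.17 lists key safety events that include "Treatment discontinuation due to adverse event" and, under the dermatological domain, "Serious or severe dermal reactions".

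**The concern.** A stopping rule for a named product risk should mean the same thing at every site. Here the same rash can be read under a section that directs stopping or under one that leaves stopping open. Section 8.2.3 is where a site would look for how to manage these events, so it could reasonably be used alone.

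What is at stake is participant safety. Section 2.3.1 reports a rash of this type in a healthy participant after a single 1 mg dose. This study gives 750 mg and then 500 mg every two weeks, and Section 2.2 puts the terminal half-life near 18 days at higher doses. A redose that should not have been given cannot be quickly reversed. A secondary matter is consistency of one safety item in SAP 6.17, since stopping treatment for a rash is itself a listed event.

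**Working it through.** The plan states no figure on this point, so the check is a comparison of the texts by type of event.

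| Event | 7.1 | 2.3.1 | 8.2.3 | Do they agree? |
|---|---|---|---|---|
| Related, severe | Should stop | Stop | May stop | No: 8.2.3 is the outlier |
| Related, mild to moderate, unresponsive to topical treatment | Should stop | Silent | May stop | No: 7.1 against 8.2.3 |
| Over 30% body surface, not severe, responding to topical treatment | Not covered | Silent | May stop | Yes: only 8.2.3 speaks |
| Unrelated, severe | Not covered | Stop (no relatedness condition) | May stop | No: 2.3.1 against 8.2.3 |
| Unrelated, not severe, unresponsive to topical treatment | Not covered | Silent | May stop | Yes: only 8.2.3 speaks |

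**Same events?** Yes. Acneiform rash is the example in 7.1 and the first event listed in 8.2.3. Section 8.2.3 has no relatedness condition, so it is wider than 7.1. It still takes in related reactions of the listed kinds that meet 7.1, and nothing confines it to events outside 7.1.

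**Same triggers?** Section 8.2.3 has three: no response to topical treatment, widespread, and severe. The first and third also appear in 7.1, where the instruction is stronger. The widespread trigger is an extra discretionary criterion and is not part of the mismatch.

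**Different strength?** Yes. Section 7.1 uses *should* for its stopping instruction on systemic hypersensitivity as well, so in that section *should* is the word for stopping. *May be considered* permits stopping without directing it.

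**When could it matter?** Infusions are given at Visits 3, 4, 5 and 6. A reaction to study drug can precede only the last three, so at most 4 − 1 = 3 infusions per participant are exposed to the ambiguity. This is an upper bound. Under the second row of the table a rash must appear, be treated and fail to respond, with doses about two weeks apart.

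**Effect on SAP 6.17.** A non-serious, mild to moderate, unresponsive rash falls outside the dermatological line, which requires a serious or severe reaction. If the site stops dosing, the participant counts under treatment discontinuation due to an adverse event. If the site continues, that item is not triggered. There are other ways into the list: study discontinuation due to an adverse event, or a moderate infusion site reaction under the hypersensitivity domain. In every case the rash is still reported as an adverse event.

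**The case against.** The strongest reply is that the sections do not strictly contradict each other. Section 8.2.3 never tells a site to continue dosing, so a site that follows 7.1 complies with both. On this reading 7.1, which carries the discontinuation heading, is the specific rule for related reactions, and 8.2.3 is a general statement about a wider set. A careful reader may well conclude that 7.1 governs, and for severe events 2.3.1 supports that. This stands as far as it goes: the risk is limited to a site acting on 8.2.3 alone. But the documents do not state that 7.1 governs, and 8.2.3 carries no pointer to it.

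A second reply is that *should* is itself weaker than *must*, which the protocol uses elsewhere (for example, for the infusion rate after a reaction in 6.1.1.2). That is true, but *should* still directs an action.

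A third reply is that the master protocol may settle the matter, since Section 7 says its discontinuation reasons and procedures must be followed. It was not available for this review. A reader might infer that sites have no governing rule at all, and the supplied documents cannot support that. They support only that the two sections read differently, and Section 7 presents 7.1 as the information specific to this drug.

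Existing controls also help: pre-dose safety review, skin examination at each visit, follow-up questions when these events are reported, and a data monitoring committee. They make an unnoticed redose less likely. They do not tell the site which instruction applies once the reaction has been found.

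**Conclusion.** The inconsistency is real and worth correcting. For related skin reactions that are severe, or mild to moderate and unresponsive to topical treatment, 7.1 directs stopping and 8.2.3 only permits it. For severe events, 2.3.1 also says to stop, and it does so regardless of relatedness, so the three places do not fully agree even beyond the related cases.

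Confidence is high that the wording differs. How often a site would act on the weaker wording, and with what harm, cannot be derived from the documents.

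Two stronger readings should be resisted. A reader might infer that inconsistent stopping would distort the efficacy comparison, but nothing in the documents allows such an effect to be derived. A reader might also infer that a mild to moderate rash reaches the SAP 6.17 list only if treatment is stopped. The study-discontinuation and infusion-site items show that this is too strong. The effect on the treatment-discontinuation count is minor and does not drive the recommendation.

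**What to change.** Replace the discontinuation sentence in Protocol 8.2.3 with:

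> *Study intervention should be discontinued for dermatological reactions meeting Section 7.1. Discontinuation may also be considered for other dermatological AEs that are widespread (>30% body surface area) or do not respond to topical treatment.*

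Then align severe events across the three places in one of two ways:

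1. Limit the mitigation in 2.3.1 to reactions related to study intervention, with a reference to 7.1. Severe unrelated events would then fall to the general discontinuation rules and the investigator's judgement.
2. State in both 7.1 and 8.2.3 that dosing stops for any severe dermatological AE, which matches 2.3.1 as it stands.

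The sponsor should choose one explicitly. Replacing the 8.2.3 sentence without this step would leave 2.3.1 out of line for severe unrelated events.

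The cost is one replaced sentence and a short matching edit, with a clarification sent to sites. No visits, procedures or participants are added, and the SAP does not need to change.

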8.1. Safety Assessments

Planned time points for all safety assessments are provided in the SoA.

8.1.1. Physical Examinations

Targeted physical examinations of skin, eyes, mouth, lungs and GI tract will be performed at each visit as described in the SoA. Any clinically significant abnormal physical examination findings will be reported as AEs.

8.1.2. Electrocardiograms

Single 12-lead ECG will be obtained as outlined in the SoA using an ECG machine that automatically calculates the heart rate and measures pulse rate, QRS, QT, and QTc.

8.1.3. Clinical Safety Laboratory Assessments

See OA01 Appendix 1 (Section 10.1) for the list of clinical laboratory tests to be performed and to the SoA for the timing and frequency for ISA OA01.

8.2. Adverse Events and Serious Adverse Events

8.2.1. Infusion Site Reactions

Symptoms of a local infusion site reaction may include erythema, induration, pain, pruritus, and edema. If an infusion site event is reported, the AE will be recorded, and additional data will be provided to the sponsor in the CRF.

Additional blood and urine samples should be collected as described in OA01 Section 10.3, Appendix 3, “Recommended Laboratory Testing for Hypersensitivity Events”. Laboratory results are provided to the sponsor via the central laboratory.

8.2.2. Hypersensitivity Reactions and Infusion-related Reactions

Many drugs, but particularly biologic agents, carry the risk of systemic hypersensitivity reactions. Drugs administered via IV infusion may lead to a systemic infusion-related reaction. If such a reaction occurs, additional data describing each symptom should be provided to the sponsor in the CRF.

Sites should have appropriately trained medical staff and appropriate medical equipment available when study participants are receiving study intervention. It is recommended that participants who experience a systemic reaction be treated per the local standard of care.

In the case of generalized urticaria or anaphylaxis, or moderate to severe infusion-related reactions, additional blood and urine samples should be collected as described in OA01

Section 10.3, Appendix 3, “Recommended Laboratory Testing for Hypersensitivity Events”. Laboratory results are provided to the sponsor via the central laboratory.

